## Aims

The aim of the study is to demonstrate the feasibility and validity of a saliva based home surveillance monitoring test for SARS-CoV-2 infection. These will be addressed in the following sub-aims.

- 1) To assess whether there is sufficient concordance between the technician and patient in interpretation of findings (Primary Feasibility Aim)
- 2) To assess sensitivity and specificity of the home saliva test (Primary Validity Aim)

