### **Primary Feasibility Outcome:**

An indicator for discrepancy in interpretation of findings by participant versus by technician via photo (interrater reliability)

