**Statistical Considerations:****General Considerations:**

We will use the Agresti-Coull method (Agresti and Coull 1998) to construct confidence intervals. Unless otherwise noted, all confidence intervals constructed will be 95% confidence intervals.

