**Analysis of the Feasibility Outcomes**

Analyses of all feasibility outcomes will be performed in the outpatient analysis set.

The concordance of the test results will be compared to the results of PCR testing. We will calculate the proportion in agreement (# of tests where SnapDx and PCR testing agree/# total tests), the proportion correctly identified as positive (# of tests SnapDx-positive/# PCR-positive), and the proportion correctly identified as negative (# of tests SnapDx-negative/# PCR-negative). A threshold of 80% overall agreement and 85% agreement in the positive tests will indicate the home test is feasible.

Percent confidence in interpretation of the results and that instructions were followed correctly will be summarized as 1) percent of respondents stating that they are at least 80% confident in their interpretation and 2) median and interquartile range of reported confidence levels. Results will be reported separately for participants and technicians.

The proportion of participants who call technical support will be presented and the frequency of the reason for the call will be presented. The proportion of tests that have a sufficient amount of saliva to reach the indicator line will be presented.

The feasibility outcomes will be presented separately by demographic characteristics in a subgroup. For example, we will evaluate whether the concordance is comparable across different age groups, between men and women, etc.

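### The feasibility verdict is tied to agreement with PCR, while the primary feasibility outcome (participant's reading versus technician's reading) has no stated analysis or success limit

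*Combined protocol and SAP*

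**What the plan says.** The Aims section gives the first aim as "To assess whether there is sufficient concordance between the technician and patient in interpretation of findings (Primary Feasibility Aim". The Primary Feasibility Outcome section makes this a binary outcome: "An indicator for discrepancy in interpretation of findings by participant versus by technician via photo (interrater reliability". The second aim is separate: "To assess sensitivity and specificity of the home saliva test (Primary Validity Aim". Analysis of the Validity Outcomes assigns it to comparison with PCR.

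Analysis of the Feasibility Outcomes opens with a general claim: "Analyses of all feasibility outcomes will be performed in the outpatient analysis set". The next sentence is "The concordance of the test results will be compared to the results of PCR testing". Three proportions follow, all with PCR as comparator, among them "the proportion correctly identified as positive (# of tests SnapDx-positive/# PCR-positive". The success rule comes next: "A threshold of 80% overall agreement and 85% agreement in the positive tests will indicate the home test is feasible". The rest of that section covers the secondary outcomes (confidence, following instructions, support calls, saliva volume) and subgroups. Technicians appear there only in connection with confidence, which is summarised separately for them and for participants.

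General Considerations names the Agresti-Coull method and adds "Unless otherwise noted, all confidence intervals constructed will be 95% confidence intervals".

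**The concern.** The section that claims to cover every feasibility outcome never says how the primary one will be analysed. It defines concordance against a different comparator and attaches the only success rule to it. What the first aim means by enough agreement between readers is not defined anywhere.

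This matters because a home test depends on lay users reading a color correctly. Under the plan as written, the trial could be declared feasible without that ever being assessed, or declared not feasible because the assay misses infections that both readers read identically. If the statistic and limit for reader agreement are chosen after the data are seen, the conclusion on the first aim is open to selection.

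**Working it through.** **Side by side**

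| | Primary feasibility outcome | Feasibility analysis and rule | Validity analysis |
|---|---|---|---|
| Compared | Participant's reading with technician's reading of photo | SnapDx with PCR | SnapDx with PCR |
| Statistic stated | None beyond a discrepancy indicator | Overall, positive and negative agreement | Sensitivity, specificity, PPV, NPV |
| Success limit | None | 80% overall, 85% in positives | None |

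The Test description section has the participant note the tube's color and then photograph it. The intended comparison is therefore a tube reading against a photo reading.

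The plan gives no sample size or power calculation for reader agreement, so there is no figure to reproduce.

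**Does the PCR rule constrain reader agreement?** If the participant agrees with PCR on a proportion *a* of tests and the technician on a proportion *b*, with *a* + *b* ≥ 1, agreement between the two lies between *a* + *b* − 1 and 1 − |*a* − *b*|. With *a* = *b* = 0.80 the range is 60% to 100%. If only the participant's reading is compared with PCR, agreement with the technician is not constrained at all.

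**Two examples.** Assumed inputs: 120 tests, 40 PCR-positive and 80 PCR-negative, with the thresholds applied to point estimates because the plan gives no interval rule. Agresti-Coull 95%: ñ = n + 3.84, p̃ = (x + 1.92)/ñ, limits p̃ ± 1.96√(p̃(1 − p̃)/ñ).

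*Example 1: readers agree, rule fails.*
- Reader agreement is 120/120: p̃ = 121.92/123.84 = 0.985, interval 96.3% to 100% (upper limit cut at 100%).
- The assay detects 24 of 40 positives with no false positives.
- Overall agreement with PCR is (24 + 80)/120 = 86.7%. Positive agreement is 24/40 = 60.0% (44.6% to 73.7%).
- 60% is below 85%, so the rule says not feasible.

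*Example 2: readers disagree, rule passes.*
- The technician matches PCR on all 120. Participants read 2 of 40 positive tubes as negative and 20 of 80 negative tubes as positive.
- Reader discrepancy is (2 + 20)/120 = 18.3%: p̃ = 23.92/123.84 = 0.193, interval 12.4% to 26.3%.
- If the technician's call is the SnapDx result: 120/120 and 40/40, both 100%.
- If the participant's call is the SnapDx result: overall (38 + 60)/120 = 98/120 = 81.7%. Positive agreement is 38/40 = 95% counting true positives only. The printed ratio does not limit its numerator to PCR-positive tests and gives (38 + 20)/40 = 145%.
- Every version meets 80% and 85%, so the rule says feasible.

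Both verdicts hold whichever reader's call counts as the SnapDx result and whichever positive ratio is used.

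**Are the data collected?** Data Acquired lists confidence surveys and an image per test, but no explicit positive/negative call for either reader. It lists the technician's evaluation only where a CLIA test was done within 24 hours. Recruitment says the low-risk group is there to assess feasibility and that some participants are not having a CLIA swab at recruitment. As listed, their photos need not get a technician reading.

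**The case against.** The strongest reply is that the analysis is implied. The outcome is a binary indicator, General Considerations supplies an interval method and level, and the feasibility section names the analysis set and calls for subgroup presentation of concordance. A discrepancy proportion with a 95% interval can be inferred. That is fair, but no section says so, the feasibility section spells out its numerators and denominators against PCR only, and nothing supplies a limit.

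A second reply is that the rule judges whether the home test is feasible, not whether readers agree, so calling an assay that finds 24 of 40 positives not feasible is no contradiction. As ordinary language that stands. It does not answer the first aim, and the detection rate belongs to the second.

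Third, example 2 is constructed. If the participant's call is the SnapDx result, three more misread tubes give 95/120 = 79.2% and the rule fails, so it does partly penalise misreading. This is true; the examples show what the rule permits, not what is likely.

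Fourth, the Rationale says participants upload results, and Handling of Missing Data refers to results they provide, so a participant call is probably stored. This largely answers the participant half of the data question. No section lists a technician positive/negative call.

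Last, the images are kept, so technician readings could be added later. That lowers the cost of the change, but does not remove the need to fix the statistic and limit beforehand.

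**Conclusion.** The concern holds, and the plan must be corrected on this point. The aim and outcome concern agreement between two readers; the stated analysis and the only success rule concern agreement with PCR. This is a mismatch in what is being judged, not only missing detail.

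In the examples, the feasibility verdict fails with complete reader agreement and passes with a discrepancy of 18.3%, nearly one test in five. The mismatch itself rests on the text alone. The sizes rest on the assumed 120 tests and 40 positives, the chosen patterns of misreading, and thresholds applied to point estimates.

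**What to change.** In Analysis of the Feasibility Outcomes:
- Make the primary analysis the proportion of tests on which the participant's reading of the tube agrees with the technician's reading of the uploaded photo, with an Agresti-Coull 95% interval.
- Pre-specify and justify a success limit, and say whether it applies to the estimate or to the lower confidence limit. For planning, with one test from each of the 120 participants in the Usability/Feasibility section, 108/120 gives 83.2% to 94.3% and 114/120 gives 89.3% to 97.9%.
- Allow for repeat tests, since Test Protocol expects one or two per bag. Two tests from each of 120 participants at 90% agreement (216/240) give 85.5% to 93.2% if treated as independent, but 83.2% to 94.3% if the pair is fully correlated (effective n = 120).
- Define the eligible tests as those a participant reads. This leaves out external samples and the tests that trained users run on other people's saliva. Missing readings among eligible tests stay under the plan's missing-data rules.

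Move the SnapDx-PCR proportions and the 80%/85% rule to Analysis of the Validity Outcomes. State there which PCR applies, because that section uses swab PCR within 24 hours and the Validity section uses saliva direct PCR. If agreement with PCR was the intended feasibility outcome, amend the Aims and Primary Feasibility Outcome sections instead.

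In Data Acquired, state that both readers' positive/negative calls are recorded, the technician's blind to the participant's, for uploaded photos whether or not a CLIA test was done within 24 hours.

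The cost is SAP wording, one justified limit, one table, and a check that both calls are stored (one field on each survey if not). The photos are already collected. The downside is technician time for reading photos without a CLIA test.

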## Study Population:

The study population consists of a diverse group of Stanford faculty, staff, and students, and the local Santa Clara County community and specific external sources with known positive saliva samples and DUA/MTA in place. More specifically, there are three sub-populations to address our aims:

- 1) (Positive population) Hospitalized patients (N=15)
- 2) (High risk and positive population) People from Bay area community and external sites with known positive saliva samples and DUA/MTA in place; Those with a suspected COVID infection seeking testing within the Stanford Health Care system (N=1500)
- 3) (Low risk population) People from Bay area community; Students on the Stanford campus and employees at Stanford Health Care (N=1500)

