## Rationale

Clinical testing for SARS-CoV-2 falls broadly into two categories: molecular testing to detect the genomic sequence of the virus and serology testing for the antibody response of the host. While CLIA based testing in both categories has proved valuable for individual care during the pandemic, the cost (up to \$100 in some cases) and time (a minimum of 12 hours in most cases) required for these approaches mean they have had little public health impact on the pandemic. A home based surveillance test for the presence of SARS-CoV-2 in saliva, that is cheap (a few dollars) and fast (under 40 minutes) would be transformative in the global management of COVID-19. It would allow nothing less than the reopening of schools, businesses, and the safe return of many aspects of society to normal. Individuals could test themselves every morning before heading to work, for example, to demonstrate they were not currently infected. In this protocol, we aim to demonstrate the viability of such an approach in a target population of Stanford employees and students who would test themselves at our research facility and upload the results via a mobile website/app. The protocol includes enrichment for positive samples through a cohort recruited through the Stanford Emergency Department (that would allow calculations of sensitivity required by the US FDA) and CLIA validation of these samples, a collection of known Sars-Cov-2 samples from external sources (including from Guatemala) as well a random selection of negative home tests to allow estimation of specificity. The overall aim is to demonstrate the feasibility, usability, and real-world validity of home surveillance testing at scale to provide the foundation for scaling up to potentially millions of tests around the world.

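### The feasibility rule sets no minimum for negative agreement, so the false-positive rate it tolerates depends on the share of PCR-positive tests recruited

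*Combined protocol and SAP*

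**What the plan says.** Analysis of the Feasibility Outcomes, in the combined protocol and SAP, defines three comparisons of SnapDx with PCR:

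- overall: "the proportion in agreement (# of tests where SnapDx and PCR testing agree/# total tests"
- positive: "the proportion correctly identified as positive (# of tests SnapDx-positive/# PCR-positive"
- negative: "the proportion correctly identified as negative (# of tests SnapDx-negative/# PCR-negative"

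The decision then uses the first two only: "A threshold of 80% overall agreement and 85% agreement in the positive tests will indicate the home test is feasible".

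The population for the rule is given in the same section: "Analyses of all feasibility outcomes will be performed in the outpatient analysis set". Study Population plans 1500 people in the high-risk and positive group and 1500 in the low-risk group. No section gives an expected number or share of PCR-positive tests.

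Negative agreement or specificity also appears in the Validity part of Study Design, in Aims, and in Analysis of the Validity Outcomes. In each place it is to be assessed or estimated, with no acceptance level.

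**The concern.** A diagnostic test makes two kinds of error, and the rule limits only one of them directly. False negatives are limited by the 85% criterion. False positives are limited only through overall agreement, which mixes both error rates in proportions set by how many PCR-positive and PCR-negative tests are in the data. Two studies of the same device could therefore reach opposite conclusions because they recruited differently. The more positives are recruited, the weaker the implied limit on false positives becomes.

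This matters because of the eventual use described in Rationale: "Individuals could test themselves every morning before heading to work". Most people testing in that way would presumably be uninfected, so the usefulness of a positive result depends heavily on specificity. As an illustration with assumed prevalences, take sensitivity 85% and specificity 80%, a pair that satisfies the rule at any mix. The positive predictive value is 0.85 × 0.01 / (0.85 × 0.01 + 0.20 × 0.99) = 4% at 1% prevalence, and 18% at 5%.

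**Working it through.** The plan derives no sample size, power or error rate for this rule, so there is no stated figure to reproduce.

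**Inputs.** The 80% and 85% thresholds and the three definitions come from Analysis of the Feasibility Outcomes. The PCR-positive share p is not in the documents, so every value of p below is an assumption. PPA and NPA are read as true agreement within PCR-positives and within PCR-negatives.

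**Step 1: what overall agreement is.** From its definition,

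overall = p × PPA + (1 − p) × NPA.

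**Step 2: an NPA of 80%.** Put NPA = 0.80: overall = 0.80 + p × (PPA − 0.80). With PPA at least 0.85 this is never below 0.80. A test wrong in 20% of PCR-negatives therefore passes at every mix.

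**Step 3: the lowest NPA that passes.** Setting overall to 0.80 gives NPA = (0.80 − p × PPA) / (1 − p).

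| Assumed p | PPA 85% | PPA 95% |
|---|---|---|
| 1% | (0.80 − 0.0085)/0.99 = 79.95% | (0.80 − 0.0095)/0.99 = 79.8% |
| 30% | (0.80 − 0.255)/0.70 = 77.9% | (0.80 − 0.285)/0.70 = 73.6% |
| 50% | (0.80 − 0.425)/0.50 = 75.0% | (0.80 − 0.475)/0.50 = 65.0% |

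Turned round, a test wrong in 25% of negatives passes once p reaches 0.05/(PPA − 0.75): 50% at PPA 85%, 33% at PPA 90% and 25% at PPA 95%.

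**Step 4: one test, two verdicts.** Take PPA 85% and NPA 78%.

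- p = 1%: 0.0085 + 0.99 × 0.78 = 78.1%, fails.
- p = 30%: 0.255 + 0.70 × 0.78 = 80.1%, passes.

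**Step 5: allowing for sampling error.** Assume 3000 independent outpatient tests, true PPA 95% and true NPA 75%, with the rule applied to point estimates. The exact binomial probability of passing is 0.00 at p = 10%, 0.09 at 20%, 0.51 at 25%, 0.93 at 30% and 1.00 at 40%.

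**Step 6: would confidence limits cure it?** The plan does not say whether the thresholds apply to the estimate or to a confidence limit. If both had to be met by the lower 95% Agresti-Coull limit (the interval named in General Considerations), with 3000 tests and PPA 95%, the tolerated error rate in negatives would still be 20.1% at p = 10%, 24.4% at 30% and 32.1% at 50%.

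**Step 7: the ratios as written.** The positive ratio counts all SnapDx-positives in its numerator, including false positives. The negative ratio counts all SnapDx-negatives, including false negatives. With sensitivity 60%, specificity 85% and p = 10%:

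- positive ratio: (0.060 + 0.135)/0.10 = 1.95
- negative ratio: (0.040 + 0.765)/0.90 = 89.4%, although specificity is 85%
- overall: 0.060 + 0.765 = 82.5%

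Taken literally, this test passes both thresholds even though it misses 40% of positives.

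**The case against.** The strongest reply is that this rule governs feasibility, not accuracy. Negative agreement is reported beside it, and specificity is part of the primary validity aim and is estimated with predictive values under Analysis of the Validity Outcomes. A poor NPA would be visible to any reader. That stands, and it confines the flaw to the decision rule.

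It is also fair that overall agreement does hold NPA close to 80% when positives are few. A reader might infer that any test wrong in 25% or more of negatives would be declared feasible. The documents do not support that: at PPA 85% it needs at least half the tests to be PCR-positive. If all 1500 + 1500 planned outpatients contributed equally, that would mean essentially the whole high-risk and positive group testing positive.

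Other tempting extensions also fail:

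- **External known-positive samples set the share.** Study Population lists their source within the high-risk and positive group, but no section clearly places them in the outpatient set used for this rule.
- **False positives accumulate over five days of home testing.** The five-day schedule in Analysis Sets is for hospitalized patients. Test Protocol expects one or two tests per bag, and nothing supports independence of daily errors.
- **Every false positive produces a study-paid swab.** Test description asks participants to take one, offers it as an option and covers its cost. It does not say that each will be taken.

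One could read the 85% criterion as the share of SnapDx-positives confirmed by PCR. That would limit false positives to about 2% of negatives at p = 10% and 15–18% at p = 50%, for PPA 85–100%. But the definition just before it uses PCR-positives as the denominator.

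Finally, a higher NPA threshold would not by itself make positive results reliable at low prevalence. With sensitivity and specificity both 85%, the positive predictive value is still 5.4% at 1% prevalence and 23% at 5%. This bears on the level to choose, not on whether NPA needs its own criterion.

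**Conclusion.** The concern holds as a defect in the stated decision rule. An error rate of 20% in PCR-negatives passes at any mix when PPA is at least 85%; this follows from the definitions alone. Higher error rates can pass, but only with enough positives or a higher PPA, so every NPA floor below 80% depends on an assumed p. The reversal for a test with PPA 85% and NPA 78% likewise rests on assumed shares of 1% and 30%. The size of the effect in this study cannot be fixed from the documents because they give no expected share. The literal wording of the positive and negative ratios is a further weakness: neither can safely carry a threshold until its numerator is corrected.

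**What to change.** In Analysis of the Feasibility Outcomes:

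1. Base the decision on two separate criteria, PPA of at least 85% and a stated minimum NPA. The sponsor should set and justify the NPA level. The plan's own 80% and 85% are natural candidates. With a minimum of 80%, any test meeting both criteria would also meet the present rule, since 0.85p + 0.80(1 − p) is never below 0.80.
2. Define the PPA numerator as tests positive on both SnapDx and PCR, and the NPA numerator as tests negative on both. The denominators stay as they are.
3. Keep overall agreement as a descriptive result, reported with the number of PCR-positive and PCR-negative tests.
4. State whether the criteria apply to the estimates or to confidence limits.

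The cost is SAP wording; the same SnapDx and PCR results supply everything needed. The downside is that the feasibility claim becomes somewhat harder to reach: the test with PPA 85% and NPA 78% that now passes at p = 30% would fail under either candidate minimum.

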### **Analysis of the Validity Outcomes**

The sensitivity, specificity, positive predictive value (PPV), and negative predictive value (NPV) of the test will be estimated using the results collected in outpatients. The results of the PCR-based test will be the gold standard used to estimate the test's diagnostic accuracy. Home test results will only be included in this analysis if the test is performed within 24 hours of the time the swab used in the PCR tests was collected.

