## Criteria for High Risk and Positive Population

### Inclusion Criteria:

- $\geq 18$  years
- Seeking testing for suspected COVID or a participant in a study of COVID-positive outpatients or from external sites with known positive saliva samples and DUA/MTA in place
- Own an internet-enabled phone or device capable of loading web pages, receiving text messages, and taking/uploading photos.
- Willing to participate in the study for one month

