## Validity

Saliva samples are to be collected in several patient populations, including from both inpatient and outpatient clinics, and COVID positive or negative patients determined by nasal swab PCR tests from several different locations. We will make a concerted effort to reach out to the Stanford and bay area communities and collect positive saliva samples from those who have tested positive through a standard PCR test. Five intended users will be given basic training to conduct SnapDx tests on these saliva samples as if they were taking the test themselves. A small portion of each saliva sample will also be tested for SARS-CoV-2 using saliva direct PCR in the laboratory. SnapDx test results will be compared against saliva direct PCR results to determine the positive percent agreement (PPA) and negative percent agreement (NPA).

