### **Recruitment:**

The study will recruit up to 3060 participants including 60 hospitalized patients from multiple locations. These will include SHC COVID testing sites, Stanford Health Care

300 and 500P locations (the Emergency Department and other in-patient wards particularly M7, the COVID ward), as well as the front entrance of Stanford hospital and several locations on Campus. We will also be recruiting folks from the bay area community for our study. Participants will fall into two categories: i) those receiving a CLIA certified nasal swab COVID-19 test at SHC at the moment of recruitment, and ii) those not.

We will be recruiting a high-risk population because we will be recruiting from a pool that includes people who are seeking medical attention and/or participating in COVID-related research studies. Feasibility and validity of the tests will be evaluated in the high-risk population. We will be additionally recruiting a low-risk population to assess feasibility in the general population. Hospitalized patients will provide information on concordance between the CLIA COVID test and the home saliva test in patients over a five day period when we expect to see a mix of positive and negative tests.

To increase the number of SARS-CoV-2 positive saliva samples, we will accept deidentified and deactivated saliva samples from external sources, including Guatemala. All of these external sources will have DUA/MTA in place and will have institutional approval and have received written informed consent from all participants for the local trials, including the sharing of these samples with Stanford University for the current trial.

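### PPV and NPV taken from an outpatient set enriched for positives, with no target prevalence stated, would reflect the recruitment mix and not home surveillance (minor)

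*Combined protocol and SAP*

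**What the plan says.** The validity analysis covers four quantities in one analysis set: "The sensitivity, specificity, positive predictive value (PPV), and negative predictive value (NPV) of the test will be estimated using the results collected in outpatients". PCR is the reference, and a home test counts only if done within 24 hours of the PCR swab. The only interval method named, under General Considerations, is Agresti-Coull, which is for a single proportion.

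On who is in the set, Recruitment says: "Feasibility and validity of the tests will be evaluated in the high-risk population". It gives the low-risk group a feasibility role, although Analysis Sets says only outpatients.

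Several routes raise the number of positives:
- The high-risk inclusion criteria admit people "Seeking testing for suspected COVID or a participant in a study of COVID-positive outpatients or from external sites with known positive saliva samples".
- The Rationale says: "The protocol includes enrichment for positive samples through a cohort recruited through the Stanford Emergency Department".
- The Validity section plans outreach to people who have already tested PCR-positive.
- Recruitment adds that "we will accept deidentified and deactivated saliva samples from external sources, including Guatemala".

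For negatives, the Rationale plans "a random selection of negative home tests to allow estimation of specificity", with no sampling fraction. Under Test description, a participant with a positive SnapDx result is asked to have a nasal swab, and one with a negative result is not.

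The Rationale and Aims give home surveillance as the purpose. No section states a surveillance prevalence, a weighting scheme or a conversion for PPV and NPV.

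**The concern.** Sensitivity and specificity are calculated within PCR-positive and PCR-negative results respectively, so the ratio of the two groups does not enter. PPV and NPV are calculated within SnapDx-positive and SnapDx-negative results, so it does. When investigators raise the number of positives through recruitment, sample PPV and NPV become partly a consequence of that choice.

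These are nevertheless the figures a reader would use to judge what one home result means. An unlabelled PPV from an enriched sample would probably make a positive surveillance result look more certain than it is. The NPV error is smaller and runs in the cautious direction.

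**Working it through.** The plan states no PPV, NPV, prevalence or specificity, so there is no figure of its own to reproduce. What follows is illustrative.

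**Inputs.** Sensitivity Se = 85%, equal to the positive-agreement threshold under Analysis of the Feasibility Outcomes but used here as an assumption. Specificity Sp = 95% or 98%, assumed. Share of positives p = 0.5% to 20%, assumed.

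**Step 1: dependence on p.**

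PPV = Se·p / [Se·p + (1 − Sp)(1 − p)]

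NPV = Sp(1 − p) / [Sp(1 − p) + (1 − Se)p]

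With Sp = 98%:
- p = 20%: PPV = 0.170 / (0.170 + 0.016) = 91.4%
- p = 1%: PPV = 0.0085 / (0.0085 + 0.0198) = 30.0%

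| p | PPV, Sp 95% | PPV, Sp 98% | NPV, Sp 98% |
|---|---|---|---|
| 0.5% | 7.9% | 17.6% | 99.9% |
| 1% | 14.7% | 30.0% | 99.8% |
| 2% | 25.8% | 46.4% | 99.7% |
| 5% | 47.2% | 69.1% | 99.2% |
| 10% | 65.4% | 82.5% | 98.3% |
| 20% | 81.0% | 91.4% | 96.3% |

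With 20% positives in the sample and 1% in use, PPV is overstated by a factor of 91.4/30.0 = 3.0 (Sp 98%) to 81.0/14.7 = 5.5 (Sp 95%). If the sample had 5% positives and use had 10%, the ratio would be 69.1/82.5 = 0.84 (Sp 98%), so the direction reverses.

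**Step 2: does a plain Bayes conversion repair this?** Only if the sensitivity and specificity fed into it are sound. The random selection of negative home tests and the swab request after a positive result both allow PCR to depend on the SnapDx result.

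Take 10,000 tests at 1% prevalence with true Se 85% and Sp 98%. They give 85 true positives, 15 false negatives, 198 false positives and 9,702 true negatives. Suppose PCR is done for all SnapDx positives and 10% of SnapDx negatives (assumed):
- Verified counts: 85 true positives, 198 false positives, 1.5 false negatives, 970.2 true negatives.
- Raw sensitivity = 85/86.5 = 98.3%; raw specificity = 970.2/1,168.2 = 83.1%.
- Bayes PPV at 1% from the raw values = 0.00983 / (0.00983 + 0.16780) = 5.5%.
- Direct PPV = 85/283 = 30.0%, which is the true value.

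Here the conversion makes PPV worse. Dividing the verified SnapDx-negative counts by 0.10 restores 15 and 9,702, and hence 85% and 98%. The conversion is therefore right only after restricting to pairs verified regardless of the SnapDx result, or after such weighting.

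**The case against.** The strongest reply is that little depends on these figures. The primary validity aim is sensitivity and specificity, the Validity section uses positive and negative percent agreement, and the only success thresholds concern overall and positive agreement. Any reader with sensitivity and specificity can convert them. This stands, and it makes the point minor. It does not remove it, because the plan chose to report PPV and NPV, and no planned output gives them at a stated prevalence with an interval.

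It can also be said that part of the enrichment may never reach this analysis. External samples are deidentified and inactivated. They may not meet the 24-hour swab rule, and may belong instead to the comparison with saliva direct PCR. That is fair: whether they enter is unclear. Test-seekers, participants in a study of COVID-positive outpatients, the Emergency Department cohort and people reached because they were PCR-positive still enrich the set.

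Third, where PCR depends only on the SnapDx result, direct PPV and NPV are unbiased for the population tested and it is raw sensitivity and specificity that go wrong. This is correct, as Step 2 shows, and it constrains the fix.

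Multiple imputation is not an answer to the prevalence question. At best it restores the recruited mix.

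A reader might infer that the plan commits to direct sample proportions. It says only that the values will be estimated; the direct reading rests on the single-proportion interval method and the absence of any conversion.

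**Conclusion.** The point holds as a minor one. PPV and NPV come from an outpatient set enriched by design, with no target prevalence, so sample values would describe the recruitment mix. PPV is overstated and NPV understated if the analysed share of positives exceeds surveillance prevalence, which the enrichment makes likely but does not guarantee. In the illustration PPV falls from 91% to 30% between 20% positives and 1% prevalence, with sensitivity 85% and specificity 98%. The accuracy values and both prevalences are assumptions.

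Two stronger conclusions might be inferred and are not supported. One is that PPV will be overstated by a known factor of three to five: the documents give neither the analysed share nor a surveillance prevalence, and the direction reverses if the first is below the second. The other is that this undermines the validity conclusion: no aim or threshold uses PPV or NPV. Verification that depends on the SnapDx result could affect raw sensitivity and specificity, but the documents only allow for it; they do not show how often it would occur.

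**What to change.** Amend Analysis of the Validity Outcomes as follows.

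1. Label PPV and NPV taken from the sample as specific to the enriched sample, and report the numbers PCR-positive and PCR-negative beside them.
2. Add a table of PPV and NPV by Bayes' rule at prespecified prevalences, for example 0.5%, 1%, 2%, 5% and 10%. Its intervals should carry the uncertainty in both sensitivity and specificity and stay defined with zero false positives or zero false negatives. A simple resampling bootstrap fails this: with zero false positives its PPV interval is 100% to 100%. A logit delta-method interval with 0.5 added to each cell is one option. Using the first eligible pair per participant is an optional way to handle repeat tests.
3. For that table, compute sensitivity and specificity only from pairs whose PCR was obtained regardless of the SnapDx result, such as people swabbed at recruitment. Alternatively, weight by the inverse of the verification fraction within SnapDx-positive and SnapDx-negative results. Weighting assumes that, given the SnapDx result, verification is unrelated to infection, so the fractions must be recorded and reported.
4. State that the table assumes accuracy carries over from the study sample, setting and operators to home users. The Rationale describes "Stanford employees and students who would test themselves at our research facility", and the Validity section says: "Five intended users will be given basic training to conduct SnapDx tests on these saliva samples".

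The cost is one paragraph and one extra table, largely from data the study already plans to collect. The drawbacks are a less favourable surveillance PPV, and fewer pairs or wider intervals after the restriction or weighting.
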